10.1 Regadenoson Study Subjects

For their time and efforts in study activities, regadenoson study subjects will receive \$200.00 for the completion of the:

- Infusion Visit and related study activities
- Complete 4 weekly telephone follow-up calls for assessment of AE's

When on-study procedures are partially completed, participants will receive \$25 remuneration.

10.2 Sickle Cell CEU Subjects

For their time and efforts in study activities, sickle cell CEU subjects will receive \$35.00 for the completion of each study visit (baseline, baseline #2, admission for pain crisis, and/or pre- and post- RBCX).

10.3 Healthy Control Study Subjects

For their time and efforts in study activities, healthy control study subjects will receive \$100.00 for the completion of the study activities and \$35 for any additional 6 hr time point CEU (optional).

When testing is partially completed, participants will receive \$25 remuneration.

10.4 Technique Optimization Control Study Subjects

For their time and efforts in study activities, technique optimization controls will receive \$25 for each contrast-enhanced ultrasound measurement visit.

10.5 Sickle Cell Control Study Subjects

For their time and efforts in study activities, sickle cell control subjects will receive \$35.00 for the completion of each CEU (0hr, 6 hr, 24hr and 30 hr).

Definity Complement Blood Sample

Subjects who provide consent and agree to give the optional Definity Complement blood sample will receive \$25 for their time and this additional blood sample.

Participants in Chicago may be offered a larger compensation amount, per the discretion of the local Principal Investigator. The amount will be based on the locally established rate of compensation for similar studies and/or procedures and must be approved by the local (UIC) IRB.

11. Adverse events

Adverse event collection and reporting is a routine part of every clinical study. All adverse events will use the descriptions and grading scales found in the CTEP Active Version of the NCI Common Terminology Criteria for Adverse Events (CTCAE).

11.1 Adverse Event Monitoring

11.1.1 Study Staff

Information on all adverse events, whether reported by the subject, directly observed, or detected by physical examination, laboratory test or other means, will be collected, recorded, followed, and reported as described in the following sections.

The PI will monitor and review adverse events monthly or more often as needed.

11.2 Definitions

Adverse Event (AE) – Any untoward or unfavorable medical occurrence in a human subject, including any abnormal sign (for example, abnormal physical exam or laboratory finding), symptom, or disease, temporally associated with the subject's participation in research, whether or not considered related to the subject's participation in research.

Serious Adverse Event (SAE) – Any adverse event temporally associated with the subject's participation in research that meets any of the following criteria:

- Results in death;
- Is life-threatening (places subject at immediate risk of death from the event as it occurs);
- Requires inpatient hospitalization or prolongation of existing hospitalization, within 48 hours of a CEU or other research-related activity (*see below);
- Results in a persistent significant/incapacity;
- Results in a congenital anomaly/birth defect; or
- Any other adverse event that, based upon appropriate medical judgment, may jeopardize the subject's health and may require medical or surgical intervention to prevent on the other outcomes listed in this definition

Note that seriousness and severity are separate concepts. The term "severe" refers to the intensity of a specific event; a severe event may be of minor medical significance (e.g., a severe leg cramp). The term "serious" is based on an outcome or action criteria that are usually associated with events that pose a threat to the patient's life or functioning. An event that is mild in severity is serious if it leads to one of the outcomes defined above.

Grade 4 and 5 events will always be considered Serious Adverse Events. Many Grade 3 and some Grade 1 and 2 events may meet the definition of a Serious Adverse Event.

* Individuals with sickle cell disease are not uncommonly hospitalized for sickle cell-related ailments, such as pain exacerbations or others, which are part of the disease process. It is important to note that any adverse event should be assessed with regard to activities that are related to research.

- **SAE's which originate from a study-related intervention, such as CEU, are most likely to occur immediately and the PI should acknowledge all hospitalizations, perceived prolongation of hospitalizations or ED visits, which occur within 48 hours of a study intervention being performed.**

Unexpected Adverse Event- Any adverse event occurring in one or more subjects in a research protocol, the nature, the severity, or frequency of which is not consistent with either:

- The known or foreseeable risk of adverse events associated with the procedures involved in the research that are described in;
 - the protocol related documents or the current IRB-approved informed consent document and;
 - other relevant sources of information, such as a product labeling or package insert or;
- The expected natural progression of any underlying disease, disorder, or condition of the subject(s) experiencing the adverse event and the subject's predisposing risk factor profile for the adverse event.

Unanticipated problem involving risks to subjects or others (UP) - Any incident, experience or outcome that meets all the following criteria:

- Unexpected (in terms of nature, severity, or frequency) given:
 - The research procedures that are described in the protocol related-documents, such the IRB-approved research protocol and the informed consent form document and,
 - The characteristics of the subject population being studied;
- Related or possibly related to the subject participation in research; and
- Suggests that the research places subjects or others at a greater risk of harm (including physical, psychological, economic, or social harm) related to the research than was previously known or recognized.

Grading of Adverse Events – Events will be graded by using the Common Terminology Criteria for Adverse Events (CTCAE) Criteria version 4.03.

Attribution – the determination and documentation of whether an adverse event is related to a medical procedure.

Attribution Categories:

1. Not Related –Event clearly related to other factors (e.g., clinical state, other therapies; concomitant drugs)
2. Possibly Related – Sequence of events is compatible with study drug, device, or procedure, but could have been produced by other factors
3. Probably Related - Sequence of event is compatible with study drug, or procedure and cannot be explained by other factors without much doubt
4. Definitely Related - Sequence of event is compatible with study drug, or procedure and beyond doubt cannot be explained by other factors

A list of the adverse events and potential risks associated with the agents administered in this study can be found in **sections 8.1-8.3**, as well as the Informed Consent Form.

11.3 Timeline for Reporting of Adverse events, Serious Adverse Events, Unexpected Adverse Events and Unanticipated Problems

All serious adverse events, all unexpected adverse events, and all unanticipated problems that occur after the initial dose of study treatment, during treatment, or during the defined follow-up period will be reported to the overall PI within 24 hours of learning of the event's occurrence by phone, email, or SAE form regardless of attribution to the study drug. A follow-up SAE report should be submitted within 24-48 hours following initial notification.

11.4 Recording Adverse Events

Participating investigators will assess the occurrence of AEs and SAEs at all participant evaluation time points during the study. All AEs and SAEs whether reported by the participant, discovered during questioning, directly observed, or detected by physical examination, laboratory test or other means, will be recorded in the participant's study and/or medical record and on the appropriate study-specific case report forms (CRFs).

11.5 Reporting Adverse Events to Institutional Review Boards

For multi-site studies where a MCW/FH investigator is serving as the principal investigator, each participating investigator is required to abide by the reporting requirements set by the MCW/FH Institutional Review Board (IRB). The study must be conducted in compliance with FDA regulations, local safety reporting requirements, and reporting requirements of the principal investigator. Each investigative site will be responsible to report SAEs that occur at that institution to their respective IRB, according to local policy. It is the responsibility of each

participating investigator to report serious adverse events to the Sponsor/ Investigator and/or others as described in Section 11.6 below.

A copy of the submitted institutional SAE form should be forwarded to:

[name]: [contact]

Study Coordinator: [contact]

The MCW/FH Principal Investigator will submit SAE reports from outside institutions to the MCW/FH IRB according to policies and procedures in reporting adverse events.

11.6 Reporting Events to the Sponsor/Investigator

11.6.1 Serious Adverse Event Reporting Requirements

All serious adverse events that occur after the initial dose of study treatment, during treatment, or during the defined follow-up period must be reported to the MCW/FH Overall Principal Investigator on the local institutional SAE form. This includes SAEs described by the criteria outlined in **section 11.2**, as well as the following:

- Grade 2 (moderate) and Grade 3 (severe) events that are unexpected and at least possibly related/associated with the intervention.
- All Grade 4 (life-threatening or disabling) events that are unexpected or not specifically listed in the protocol as not requiring reporting.
- All Grade 5 (fatal) events while the participant is enrolled and actively participating in the trial **OR** when the event occurs during the defined follow-up period of the last study intervention.

Participating investigators must report each serious adverse event to the Overall Principal Investigator within 24 hours of learning of the occurrence. In the event that the participating investigator does not become aware of the serious adverse event immediately (e.g., participant sought treatment elsewhere), the participating investigator is to report the event within 24 hours after learning of it and document the time of his or her first awareness of the adverse event. Report serious adverse events by email or telephone to:

[name]

[contact]

[contact]

Email is preferred; however, in urgent situations after normal business hours, the Principal Investigator can be reached at [contact]

Within 24-48 hours, the participating investigator must provide follow-up information on the serious adverse event, utilizing the appropriate SAE Reporting Form. Follow-up information should describe whether the event has resolved or continues, if and

how the event was treated, and whether the participant will continue or discontinue study participation.

Follow-up reports should be emailed to [name] at the email address above and to the study coordinator at [contact]

11.6.2 Non-Serious Adverse Event Reporting Requirements

Non-serious adverse events will be reported to the Principal Investigator on the toxicity Case Report Forms.

11.6 Food and Drug Administration (FDA) Notification by Sponsor/ Investigator for Investigational Agent

The Sponsor-Investigator will report to the FDA any adverse event that is serious, unexpected and reasonably related (i.e., possible, probable, definite) to the investigational study treatment.

Unexpected fatal or life-threatening experiences associated with the use of the investigational study treatment will be reported to FDA as soon as possible but in no event later than 7 calendar days after initial receipt of the information.

All other serious unexpected experiences associated with the use of the investigational study treatment will be reported to FDA as soon as possible but in no event later than 15 calendar days after initial receipt of the information.

Events will be reported to the FDA by telephone ([name]) or by fax ([name]) using Form FDA 3500A (Mandatory Reporting Form for investigational agents). Forms are available at <http://www.fda.gov/medwatch/getforms.htm>.

12. Data and Safety Monitoring

12.1 Data Management and Collection

Research information, including consent forms and will be maintained secure as described in the Confidentiality **section 13.3**.

Data will be collected onto study-specific case report forms. The data gathered will be entered into an electronic data set maintained by the investigator. Each participant will have a unique identifier, or study ID, assigned. This study ID will be used to label all shipped biological specimens. All data and samples will be coded with their respective unique identifier. Only the study coordinator and investigator will have access to the study ID key. The study coordinator will also retain all source documentation for each subject, which will be stored in locked cabinets, inside a locked secured building.

12.2 Data Safety Monitoring Board (DSMB)

The overall study principal investigator will appoint at least three physicians and/or scientists with research experience as members of the DSMB group. They will monitor accruing data in order to confirm that the patients in the trial are being cared for safely, and make recommendations as appropriate. The DSMB will be responsible for:

- 1) Reviewing and analyzing the progress of the study;
- 2) Reviewing recruitment and event rates.
- 3) Approving amendments to the trial protocol, if warranted;
- 4) Monitoring the risk/benefit ratio, safety and response of study treatments and diagnostic procedures;
- 5) Ensuring complete and responsible reporting and data quality;
- 6) Approving amendments to the trial protocol, if warranted;
- 7) Consult with the site monitor physician as needed
- 8) Provide a summary of their findings in a written report

The DSMB will meet at least annually by phone, or in person, or more often if warranted to review serious adverse events.

Local Data Safety Monitoring Plan -The local principal investigator and/or members of the research team will monitor the study for regulatory compliance, inclusion/exclusion criteria, accrual/withdrawal rates, and breach of confidentiality annually prior to submission to the IRB. Any adverse events will be reviewed immediately with the Principal Investigator and will be reported to the local respective IRB per site IRB regulations. All study events will be summarized once a year for the IRB, during annual continuing review progress report.

The local IRB will determine when it is necessary to inform participants of any new findings that reveal additional risk or information that may alter their willingness to participate in the trial.

13. Human Subjects Protection

13.1 Informed Consent

Subjects are required to sign an informed consent prior to screening, and before undergoing any study procedures or assessments, in accordance with ICH E6; 4.8, "Informed Consent of Trial Subjects." When substantial modifications are made to the informed consent, the IRB may require that all subjects currently enrolled in the study will be re-consented; ICH E6; 4.8 guidelines would still apply.

Subjects will be provided with a copy of the signed informed consent form used in the study, procedures, and assessments. Subjects will also be provided with the contact telephone numbers of the investigator and qualified personnel who can assist with their questions and concerns.

13.2 Protected Health Information

Protected health information that will be collected as part of this study includes name, date of birth, dates for hospitalization, and medical, diagnostic history and medications (as mentioned in **Sections 5 and 6**). This information will be stored for 3 years beyond the completion of the study. After blood is used for study testing it will be discarded.

13.3 Confidentiality

Loss of confidentiality is always a potential risk when collecting protected health information. Research Records will remain confidential. Volunteer subject's records will be available to the study staff and to each site's IRB and for audit purposes. Only authorized personnel will have access to the protected health information and research records. In order that confidentiality can be maintained, the principal investigators will keep records in locked cabinets/room and results of tests will be coded to prevent association with volunteers' names. All electronic data will be entered into a secured data set that is password protected. Identifying information will not be included on laboratory samples, faxes, or correspondence. Laboratory samples will be shipped with only unique study numbers that will be linked to a key kept by the site Principal Investigator.

All study team members are trained in HIPAA privacy regulations and other applicable site privacy policies. No information will be released, nor will participation

in the research be acknowledged, to any party except where compulsory according to law or intuitional policy. The results of the research study may be published, but volunteers' names or identities will not be revealed.

13.4 Follow-up and Record Retention

The current proposal involves on-going data collection for the duration of the study at each site. The records will be maintained per site policy but at a minimum of two years per FDA requirements.

14. Statistical Considerations

14.1 Description of Endpoints:

14.1.1 Primary Endpoint: Primary outcome measure will be a 40% increase in skeletal muscle microvascular blood flow when 24 hour measurements are compared to baseline in subjects receiving regadenoson.

14.1.2 Secondary Endpoints:

- Secondary outcome measure will be that there will be more complement deposited on lipid microbubbles from the plasma from the subjects with SCD who suffered pain events compared to the other groups.
- Secondary outcome measure will be a 40% increase in skeletal muscle microvascular blood flow when 12 week measurements are compared to baseline in subjects receiving hydroxyurea.
- Decrease in iNKT cell activation as measured by NFkB when 24 hour measurements are compared to baseline in subjects receiving regadenoson.

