The ultimate goal in studying regadenoson is to improve vaso-occlusion and dampen the severity of vaso-occlusive episodes. Regadenoson's mechanism in sickle cell disease is to inhibit iNKT cell activation thereby decreasing inflammation that contributes to white blood cell, platelet and endothelial cell activation. Decreasing inflammation and interrupting the multi-cellular interactions of vaso-occlusion should result in increased blood flow. If blood flow is not increased following regadenoson, it is unlikely to provide clinical benefit in reducing the severity of pain or acute chest syndrome episodes. For this proposal, we will quantify regional perfusion in the skeletal muscle and myocardium in sickle cell disease subjects using contrast-enhanced ultrasound.

2. Study Objectives

2.1 Primary Objective: To determine changes in microvascular blood flow using contrast-enhanced ultrasound (CEU) in 27 adults age 18 years or older with sickle cell anemia before, during and after a 24 hour infusion of regadenoson.

2.2 Secondary Objectives:

- **To determine the association between complement deposition on lipid microbubbles and pain events associated with Definity in adults with SCD.**
- To examine differences in microvascular blood flow using contrast-enhanced ultrasound (CEU) in adults with sickle cell anemia age 18 and older at baseline compared to healthy, African American controls.

- To examine differences in microvascular blood flow using contrast-enhanced ultrasound (CEU) in adults with sickle cell anemia age 18 and older at baseline state compared to a pain crisis.
- To evaluate the activation of iNKT cells before, during and after regadenoson

3. Study Population

The study population will consist of four study groups, and one technique optimization control group:

- Regadenoson treatment group
- Sickle Cell CEU measurement group
- Healthy Control subjects group
- Technique Optimization Control subjects group
- Sickle Cell Control group

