9.7 Exploratory Study of complement deposition on Definity microbubbles in vivo (optional)

Complement deposition on the surface of lipid microbubbles will be compared between samples collected in subjects with SCD who had pain events associated with Definity (n=4), patients SCD who did not have a pain event (n=10) and healthy African American controls (n=10). We will collect up to 4ml whole blood into anticoagulated tubes, and spin for plasma, transfer to anonymized cryovials, and store at -80C until ready for analysis. Samples will be analyzed at the laboratory of [name] in Portland, OR.

In [name] laboratory in Portland, plasma will be incubated with lipid microbubbles and then flow cytometry will be performed to measure surface complement deposition on the microbubbles. Approximately 4ml blood will also be collected for isolation of serum and analyzed for levels of circulating complement (C3, C4, CH50) at a clinical laboratory.

10. Subject Remuneration

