14.2 Statistical Analysis

Primary outcome measure: change in skeletal muscle microvascular blood flow during regadenoson infusion, obtained at baseline and at end of infusion (24 hours); Secondary outcome measures: myocardial microvascular blood flow, functional microvascular density, reduction in iNKT cell activity (as measured by phospho-NF-kB expression).

We anticipate that at baseline sickle cell disease subjects will have skeletal muscle blood flow similar to that of subjects with diabetes who are hyperemic, for whom data suggests a mean blood flow of 0.7 (standard deviation 0.3) ³⁰. We seek to detect a 30% increase from baseline in skeletal muscle microvascular blood flow, to a mean of 1.0, following the administration of regadenoson (Aim 1). With 27 patients enrolled on the 24 hour regadenoson study of Aim 1, we will have 90% power to

detect this difference, testing at the one-sided 0.05 significance level. For these calculations we assume that the unknown correlation of measurements within patient is positive, and that therefore the maximum value for the variance of the difference will be two times the variance of a single observation, or 0.18 (standard deviation 0.42). Secondary outcome measures will be summarized and differences assessed for regadenoson therapy, and tested with the one-sample t-test if symmetry holds and the Wilcoxon signed rank test if it does not. Serial measures of iNKT cell number and activation state and markers of inflammation will be obtained during therapy. We will construct longitudinal mixed models of these outcomes, controlling for demographic factors.

Since we do not know the magnitude of complement deposition on the lipid microbubbles in this setting, power calculations will use the Wilcoxon rank sum test, assessing number of standard deviations of difference. We will have 87% power to detect a 1.5 standard deviation difference and 80% power to detect a 1 standard deviation difference in complement deposition between the subjects who did and did not have reactions, testing at the 0.10 one-sided significance level.

References

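### The complement endpoint uses a broader comparator than the within-SCD objective it serves, and no rule says which contrast decides

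*Combined protocol and SAP*

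**What the plan says.** Section 2.2 gives the objective: "To determine the association between complement deposition on lipid microbubbles and pain events associated with Definity in adults with SCD". This is a question within one disease population.

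Section 14.1.2 defines the matching endpoint: "there will be more complement deposited on lipid microbubbles from the plasma from the subjects with SCD who suffered pain events compared to the other". The sentence ends on a plural comparator, and the section does not name the groups.

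Section 9.7 does name them. The index group is "subjects with SCD who had pain events associated with Definity (n=4"), and the comparators are "patients SCD who did not have a pain event (n=10) and healthy African American controls (n=10").

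Section 14.2 gives power for a difference "between the subjects who did and did not have reactions", "testing at the 0.10 one-sided significance level", and claims 87% at 1.5 SD and 80% at 1 SD. It names the Wilcoxon rank sum test for the power calculation only. It does not say whether healthy controls count among those without reactions, and it gives no rule for handling three groups.

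**The concern.** A reactor differs from an SCD non-reactor in the reaction. A reactor differs from a healthy control in the reaction and in having SCD. Only the first comparison answers objective 2.2, yet the endpoint sets reactors against both groups without saying how the two comparisons combine.

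Three rules would fit the endpoint wording: a positive result against either group, a positive result against both, or one test against the two groups pooled. They can give different answers from the same 24 samples. Under the first and third, a general difference between SCD and healthy plasma could be reported as support for a complement mechanism of Definity pain. Under the second, the chance of detecting a real reaction effect depends on a disease difference that the objective does not ask about.

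**Working it through.** **Inputs from the documents.** Group sizes 4, 10 and 10 (section 9.7). Rank sum test, one-sided 0.10, effects of 1 and 1.5 SD, stated power 80% and 87% (section 14.2).

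**Assumptions.** Normal data with equal SD. The SCD-minus-healthy shift is not in the documents, so it is varied from -0.5 to 1.5 SD.

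**Step 1: the plan's own power.** Approximate rank sum power comes from a noncentral t distribution with m+n-2 degrees of freedom and noncentrality d × √(3/π) / √(1/m + 1/n), where √(3/π) = 0.977.

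- 4 v 10, d = 1.5: 1.5 × 0.977 / √0.35 = 2.48, critical t (12 df) 1.356, power 86.6%. The stated 87% reproduces.
- 4 v 10, d = 1: noncentrality 1.65, power 62.3%. The stated 80% does not reproduce.
- 4 v 20, d = 1.5 and 1: about 91% and 68%. Neither stated figure reproduces.

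Using the exact test, simulated power for 4 v 10 is 84.7% at 1.5 SD and 59.9% at 1 SD. Across all the formulas tried, power at 1 SD is 59–66% for 4 v 10 and 64–71% for 4 v 20. A 10 v 10 comparison gives 80.3% at 1 SD, but the plan does not say that the 80% came from there.

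**Step 2: exact critical values.** For 4 v 10 there are C(14,4) = 1001 rank sets. A reactor rank sum of 40 or more occurs in 94 of them, so the size is 94/1001 = 0.0939. For 4 v 20 there are C(24,4) = 10,626 sets. A sum of 68 or more occurs in 970, so the size is 970/10,626 = 0.0913.

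**Step 3: false positives when there is no reaction effect** (200,000 simulated trials per scenario, % positive).

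| SCD minus healthy (SD) | Reactor v SCD non-reactor | Either contrast | Pooled 4 v 20 | Both contrasts |
|---|---|---|---|---|
| 0 | 9.4 | 14.7 | 9.0 | 4.1 |
| 0.5 | 9.4 | 31.6 | 17.8 | 7.5 |
| 1.0 | 9.3 | 60.0 | 28.5 | 9.0 |
| 1.5 | 9.4 | 84.7 | 39.6 | 9.4 |

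**Step 4: power at a true 1 SD reaction effect** (%).

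| SCD minus healthy (SD) | Reactor v SCD non-reactor | Both contrasts |
|---|---|---|
| -0.5 | 60 | 27 |
| 0 | 60 | 47 |
| 0.5 | 60 | 58 |
| 1.0 | 60 | 60 |

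The within-SCD contrast is the only one whose error rate and power do not move with the disease shift.

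**The case against.** The documents lean towards the within-SCD contrast. The objective is confined to adults with SCD, section 14.2 attaches its one-sided 0.10 to a single contrast, and the 87% fits 4 v 10 but not 4 v 20. This stands as partial evidence. It does not settle the matter, because the 80% in the same sentence fits neither, and the endpoint that defines success still names a wider comparator.

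A reader might infer that the plan, as written, lets a plain SCD-versus-healthy difference pass as an association with pain. The documents do not support so strong a reading. No section proposes pooling or lets reactors versus healthy controls decide alone, and section 9.7 lists three separate groups. More deposition than the other groups can naturally be read as more than each of them, and that reading holds false positives at about 9% or less. What remains is that the plan does not state this rule. The rule also costs power unless SCD plasma has the higher deposition; the largest loss shown, to 27%, needs SCD plasma to have the lower deposition, for which the documents give no ground.

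Pooling also has an advantage: if there is no disease difference, the exact 4 v 20 test has about 65% power at 1 SD against 60%. That gain depends on an assumption the plan has no data to support.

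Finally, section 9.7 labels the work exploratory and optional, with four reactors. That limits the stakes. It is nevertheless the first-listed secondary objective and secondary endpoint, with a stated significance level and power.

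**Conclusion.** The point holds as a mismatch between objective and endpoint, combined with a missing decision rule. Under the either rule, a disease shift of 0.5 to 1.5 SD alone makes the endpoint positive in about 32 to 85% of trials; under pooling, in about 18 to 40%. Under the both rule there is no excess of false positives, but power at 1 SD is about 27 to 60% across shifts of -0.5 to 1.0 SD, against a constant 60% for the within-SCD contrast. The shift sizes, normality and equal SDs are assumptions. The mismatch itself rests on the text alone.

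Separately, the stated 80% at 1 SD is not correct for 4 v 10 by any formula tried. The primary endpoint is unaffected. The change should be made, but it is a clarification and not a threat to the trial.

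**What to change.** - **Section 14.1.2:** replace the reference to the other groups with *compared with subjects with SCD who had no pain event*.
- **Section 14.2, contrast:** name reactors (n=4) versus SCD non-reactors (n=10), by rank sum test at one-sided 0.10, as the single deciding contrast. Present the healthy controls as a descriptive reference, not pooled with the non-reactors.
- **Section 14.2, power:** restate it for that contrast as about 85–87% at 1.5 SD and about 60% at 1 SD.

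This needs protocol wording only, with no new samples or subjects. The small downside is that a difference between reactors and healthy controls no longer supports the endpoint by itself, and the possible power gain from pooling is given up.
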